9.3.2 Labeling of blood samples

Label tubes with COH protocol #, subject ID (issued by DCC), institution (for non-COH sites), date and actual timepoint of collection (e.g. D1C1 for Day1 of Cycle 1), and if applicable patient initials.

9.3.3 Blood collection

9.3.3.1 Notifying the receiving laboratory

Before a scheduled blood collection (at least one day in advance) e-mail [name] ([contact]) or [name] ([contact]) at the Analytical Pharmacology Core Facility (APCF) to inform them of a pending collection.

9.3.3.2 Order of draw for the research blood samples

Please draw purple-top/ Cell-free DNA BCT® (Streck) tubes before the green-top tubes.

Any heparin in the collection tube of the line used to draw the blood in a purple tube/ Cell-free DNA BCT® tube will make it unusable.

If a purple tube/ Cell-Free DNA BCT tube immediately follows a heparin (green-top) tube in the draw order (for example if the last clinical/non-research sample was collected in a green-top tube), please collect a non-additive or EDTA tube as a waste tube prior to collection in the purple tube/ Cell-Free DNA BCT tube.

If applicable, Cell-Free DNA BCT tubes can also be drawn after the EDTA tube and before the fluoride oxalate (glycolytic inhibitor) tube.

9.3.3.3 Collection and post-collection guidelines

Refer to [Table 9.3.3](#) for collection and post-collection instructions.

Refer to [Appendix I](#) and [Appendix J](#) for blood collection form and blood shipping guidelines, respectively.

Table 9.3.3. Blood sample collection and post-collection instructions.

Tube Type	Collection details	Site of collection	Post-collection instructions
Green-top	1- Blood samples will be collected from an indwelling venous catheter or by venipuncture. 2- Invert tubes eight times after collection. 3- Immediately place the tubes on ice .	COH	Promptly deliver the blood samples on ice to the APCF, [name] for processing within 4 hours .
		Non-COH	Ship overnight at $\sim +4^{\circ}\text{C}$ to APCF laboratory. See Appendix J . Include with shipment: - Blood sample collection form (Appendix I). - Copy of latest CBC results (with differential) and date of test.
Purple-top	Same as for green-top.	COH Only	Promptly deliver the blood samples on ice to the APCF, [name] for processing within 4 hours .
Cell-free DNA BCT® (Streck)*	1- Blood samples will be collected from an indwelling venous catheter or by venipuncture. Prevention of backflow: (Because cell-free DNA BCT® contain chemical additives) a. Keep patient's arm in the downward position during the collection procedure. b. Hold the tube with the stopper in the uppermost position so that the tube contents do not touch the stopper or the end of the needle during sample collection. c. Release tourniquet once blood starts to flow in the tube, or within 2 minutes of application. 2- Fill tube completely. 3- Remove tube from adapter and immediately mix by gentle inversion 8 to 10 times. 4- Do not freeze samples. Store samples at 18-25°C until shipment.	Non-COH Sites only	Ship to APCF laboratory. See Appendix J . Include with shipment: - Blood sample collection form (Appendix I). - Copy of latest CBC results (with differential) and date of test.

* Tubes are stable when stored at 2-30°C through expiration date. Do not use expired tubes. If there is any indication of cloudiness or visible precipitate immediately contact the COH Data Coordinating Center (DCC). Contact information: E-mail: [contact].

9.3.4 Sample Processing by APCF (COH)

All blood samples will be processed at COH APCF. External (non-COH) sites will only be expected to collect and ship whole blood to COH APCF.

Blood samples will be kept on a rocker set at low speed to mimic circulation and avoid clot formation until processing.

Green-top tubes (PBMCs AND plasma), for FACS/Cytokine assays:

(Process within 4h of collection for COH samples OR upon receipt of non-COH samples).

• Centrifuge for 10 min at 1800g at 4°C. Both supernatant and pellet will be used.

• Plasma:

- The resulting upper plasma layer from each tube will be drawn up sequentially into a sterile 5 mL syringe and pushed through a sterile 0.2/0.8 micron disposable filter.
- The filtered plasma will then be transferred in 500 µL aliquots into multiple appropriately-labeled Starstedt microfuge tubes.
- To one aliquot, add 0.5 mL glycerol/0.02% sodium azide solution to dilute the plasma 50/50 v/v. Keep the diluted plasma sample at -20°C and do not freeze.
- All the remaining plasma aliquots will be stored frozen at -80°C until ready for testing.

• PBMCs:

- Dilute the blood remaining in the green-top tubes used to prepare plasma above 1:1 with Hank's Balanced Salt Solution (or equivalent) in a sterile conical centrifuge tube.
- Isolate PBMCs by Ficoll-gradient separation per COH APCF procedures.
- PBMCs samples will be stored in liquid nitrogen until use.

Purple-top and Cell-free BCT tubes (Plasma and PDWB), for sequencing assays:

Purple-top (~20 mL) (Collected from COH patients only)	Plasma and Plasma depleted whole blood cells (PDWB)	
 1. Centrifuge for 10 minutes at 1800 x g at 4°C. 2. Remove the tubes from the centrifuge. Do not disturb the cellular layer. 3. Extract plasma carefully. 
 a. Do not disturb the buffy coat while pipetting plasma; leave ~3-4mm of plasma behind to ensure the buffy coat is undisturbed. b. Save the PDWB portion (see below). 4. Freeze plasma at -80°C in 1-2mL aliquots. Do not fill tubes beyond 70% capacity. 5. Mix the remaining PDWB. 6. Freeze at -80°C in 1-2mL aliquots.
---	---	--

Cell-free DNA BCT (~20 mL) (Collected from non-COH patients only)	Plasma and Plasma depleted whole blood cells (PDWB)	
 1. Centrifuge for 10 minutes at 1600 x g at room temperature. 2. Remove the upper plasma layer and transfer to a new conical tube. Save the PDWB portion (see below). 3. Centrifuge the plasma at 16000 x g for 10 minutes. 4. Collect the plasma. 5. Freeze plasma at -80°C in 1-2mL aliquots. Do not fill tubes beyond 70% capacity. 6. Mix the remaining PDWB. 7. Freeze at -80°C in 1-2mL aliquots.
--	---	---

10.0 STUDY CALENDAR

All procedures may increase in frequency if clinically indicated.

Table 10 Study Activity Calendar

Protocol Activity	Screening (Days) -28 to D1)	Protocol Therapy (Cycles) ^{a, c, m} (± 3 Days for all time points except g)														EOT ^p	Follow-up ^w			
		To be repeated (except e and l)							Safety post ^b								Response ^q (Every 12 weeks)		Survival ^r (Every 12 weeks)	
		1		2		3		4		5		6		7						
		D1	D8	D1	D8	D1	D8	D1	D8	D15 ^g	D1	D8	D1	D8	D1	D8				
Informed Consent	X																			
Eligibility Criteria	X																			
Registration	X																			
Medical History	X																			
Prior and Con. Med. review	X	X	X	X	X	X	X	X	X		X	X	X	X	X	X	X			
Post-study anti-cancer ther. status																	X	X	X	
Survival status		X	X	X	X	X	X	X	X		X	X	X	X	X	X	X	X	X	
Pembrolizumab		X		X		X		X			X		X		X					
Pralatrexate		X	X	X	X	X	X	X	X		X	X	X	X	X	X				
Leucovorin ^d		X	X	X	X	X	X	X	X		X	X	X	X	X	X				
Vitamin B12 ^e	X							X												
Folic acid ⁿ	X							X												
AE review		X	X	X	X	X	X	X	X		X	X	X	X	X	X	X	X		
Physical Exam.	X	X	X	X	X	X	X	X	X		X	X	X	X	X	X	X	X		
Vital signs ^f	X	X	X	X	X	X	X	X	X		X	X	X	X	X	X	X	X		
ECOG status	X	X	X	X	X	X	X	X	X		X	X	X	X	X	X	X	X		
Pregnancy Test ^o	X ^k	X		X		X		X			X		X		X		X	X ^s		
PT/INR and aPPT	X*																			
CBC w/diff, Plt	X*	X	X	X	X	X	X	X	X		X	X	X	X	X	X	X	X		
Serum Chemistry ^u	X*	X	X	X	X	X	X	X	X		X	X	X	X	X	X	X	X		

CONFIDENTIAL

Protocol Activity	Screening (Days -28 to D1)	Protocol Therapy (Cycles) ^{a, m} (± 3 Days for all time points except g)														EOT ^p	Follow-up ^w			
		To be repeated (except e and l)							Safety post ^b								Response ^q (Every 12 weeks)		Survival ^z (Every 12 weeks)	
		1		2		3		4		5		6		7						
		D1	D8	D1	D8	D1	D8	D1	D8	D15 ^g	D1	D8	D1	D8	D1					
Urinalysis ^x	x [*]																			
Thyroid Test ^v		x			x					x						x				
PET-CT or CT N/C/A/P ^h	x								x							x ^r		x		
Archival or Newly Obtained Tumor Tissue Collection	x ⁱ															x ⁱ				
Bone Marrow Aspirate and Biopsy ^j	x ^y							x ^l		x ^l						x ^t				
Correlative Blood Collection		x	x					x ^l		x ^l										

* Tests to be performed within 28 days of treatment initiation.

- In the absence of a delay due to toxicity, each treatment cycle lasts 21 days ± 3 days.
- Safety visit to occur 30 (-2/+7) days post-last dose of protocol therapy. At the end of the treatment, each subject will be followed for 30 days for adverse event monitoring, and 90 days for severe adverse events and events of clinical interest. Safety follow up may be extended until resolution/stabilization of reportable AEs.
- Protocol therapy will continue for a maximum of 24 months until progressive disease, unacceptable toxicity, withdrawal of consent, pregnancy of the subject, non-compliance, or administrative reasons.
- Leucovorin will be administered orally three times daily (every 8 hours) for 2 days for a total of 6 doses **beginning 24h (+/- 2h) after each dose of pralatrexate** is administered. Refer to [Section 5.13.2](#).
- Vitamin B12 (1 mg IM) will be administered anytime within 10 weeks prior to initiation of pralatrexate (per pralatrexate product insert) and can be administered during screening, and will be administered every 3 cycles. Administration should continue during the full course of pralatrexate therapy and for 30 days after the last dose of pralatrexate. Refer to [Section 5.13.2](#).
- Vital signs: Weight, heart rate, blood pressure, respiration rate, and temperature. Height required only at baseline.
- To be done between D15 and D21 (-3 days).

- h. Disease staging is performed at screening and every 4 cycles until disease progression or off study therapy. Disease staging will be by either PET/CT (preferred) or CT scan, but, in patients with FDG-avid disease, it will be preferred (but not mandatory) to have PET/CT at baseline, Cycle 4 and every 8 cycles thereafter. Note: if there is no evidence of neck involvement by lymphoma at baseline, CT of chest, abdomen and pelvis (C/A/P) can be performed instead of N/C/A/P at subsequent re-staging.
- i. Tumor biopsy tissue will be obtained after routine diagnostic biopsy is done with the patient's consent. Exception can be granted by the PI if a biopsy is not feasible and/or safe. For the EOT time point, tumor tissue will be collected from a standard of care tumor biopsy performed at the time of lymphoma relapse/progression (if such a biopsy is performed), unless the tumor is inaccessible or there is a safety concern.
- j. Following initial screening, and unless clinically indicated, bone marrow specimens will be collected only to confirm CR.
- k. Female subjects of childbearing potential should have a negative urine or serum pregnancy within 72 hours prior to receiving the first dose of study medication.
- l. Do not repeat this time point for correlative blood collection: peripheral blood is collected prior to study treatment/procedures on C1D1, C2D1, C4D1, C5D1, and at EOT (see also footnote t).
- m. Day 8 labs/visits are set up because of pralatrexate administration on these days. If a patient discontinues pralatrexate (and continues with pembrolizumab alone), these Day 8 labs/visits can be omitted.
- n. Folic acid supplementation is to begin within 10 days (as early as possible) prior to the first dose of pralatrexate administration (per pralatrexate product insert). However, if folic acid was not taken but MMA (methylmalonic acid) and HCY (homocysteine) levels were checked and are in normal range at screening, the investigator can decide to start study therapy immediately. Administration should continue during the full course of pralatrexate therapy and for 30 days after the last dose of pralatrexate. Refer to [Section 5.13.2](#).
- o. If the urine test is positive or cannot be confirmed as negative, a serum pregnancy test will be required. Pregnancy testing will also be performed whenever an expected menstrual cycle is missed or when pregnancy is otherwise suspected.
- p. Assessments to be performed within 10 days of treatment discontinuation (except tumor imaging, see footnote r). Assessments performed after last dose of study agent and within 7 days of the decision to end treatment may serve as EOT assessments.
- q. For participants yet to progress. Follow-up will occur every 12 weeks (-/+ 7 days) starting from last on-treatment scan. After one year, the imaging time point will occur every 18 weeks (+/- 7 days). Response Follow-up will be performed until progression or off study, and for at least one year in each patient who did not progress yet.
- r. PET-CT (or CT) at time of discontinuation (EOT) will only be performed in patients who discontinue treatment for disease progression. Note: if a previous scan was obtained within 4 weeks prior to the date of discontinuation, then repeating the scan at treatment discontinuation is not mandatory. For patients who discontinue treatment for other reasons than disease progression (e.g. for toxicity, CR): PET-CT (or CT) will not be performed at EOT and will be performed 12 weeks

after their last scan, and according to the follow-up schedule thereafter (refer to footnote q for the frequency of scans during the follow-up period).

- s. Pregnancy test will be performed at the safety visit (30 days post last dose of protocol therapy).
- t. EOT time point: correlative blood will not be collected if a correlative blood sample for ctDNA/MRD (purple-top/cell-free DNA BCT® tube) was collected within the prior 8 weeks.
- u. Serum chemistry panel to include: glucose, Blood Urea Nitrogen (BUN), creatinine, uric acid, total protein, albumin, magnesium, calcium, inorganic phosphorus, sodium, potassium, chloride, total CO₂ or bicarbonate, total bilirubin, direct bilirubin (if total bilirubin is elevated above the upper limit of normal), alkaline phosphatase, ALT, AST, and LDH.
- v. Thyroid test includes TSH only.
- w. Please refer to [Section 5.11](#) for details about the Follow-up period.
- x. Urinalysis to include blood, glucose, protein, specific gravity, and microscopic exam (if abnormal).
- y. Bone marrow biopsy at screening is not mandatory, and should only be performed if clinically indicated (e.g. for cytopenias).
- z. Participants who end Response Follow-up will enter Survival Follow-up. Survival assessment to occur bi-annually or as requested by the Study PI via medical record review, review of social security registry, or telephone call.

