11.0 ENDPOINT EVALUATION CRITERIA/MEASUREMENT OF EFFECT

11.1 Response/Progression

Disease response/progression will be evaluated using 2014 Lugano Classification (see [Appendix B](#))^{8,11}. Participants who meet the definition of progressive disease per Lugano Classification should be evaluated using the LYRIC criteria¹⁰ (see [Appendix C](#)). The ORR and CR rate will also be estimated according to the International Harmonization Project response criteria (Cheson 2007).⁹

PET-CT or diagnostic quality CT of the neck, chest, abdomen, and pelvis (N/C/A/P) with IV contrast will be performed at baseline (within the screening window, 28 days) prior to initiation of study therapy, and then after initiation of study therapy during cycle 4 and every 4 cycles thereafter until disease progression or off study therapy. Refer to [study calendar \(footnote r\)](#) for disease staging at EOT. Disease staging will be by either PET/CT (preferred) or CT scan, but, in patients with FDG-avid disease, it will be preferred (but not mandatory) to have PET/CT at baseline, Cycle 4 and at least every 8 cycles thereafter. In patients with FDG-avid disease, CR must be confirmed with PET/CT. Patients who enter CR with study therapy can be monitored with diagnostic quality CT scans thereafter until disease progression. MRI may be performed at the investigator's discretion for lesions not well-visualized by CT, or if CT with intravenous contrast is contraindicated. PET-CT and CT results will be read by radiology at each study site and investigator response based on radiology reading will be performed. Lymphoma response assessment based on PET-CT/CT will be based on the 2014 Lugano Classification ([Appendix B](#)).^{8,11}

Note: if there is no evidence of neck involvement by lymphoma at baseline, CT of chest, abdomen and pelvis (C/A/P) can be performed instead of N/C/A/P at subsequent re-staging.

Following initial screening, and unless clinically indicated, bone marrow specimens will be collected only to confirm CR.

For patients with progression of disease on imaging, it is strongly recommended that a confirmatory biopsy (performed as standard of care) be obtained whenever possible. Note that only an FDG-negative PET scan will be considered complete remission in patients whose tumor was FDG-avid at baseline.

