11.2 Clinical Endpoint Definitions

Overall Response Rate (ORR): Defined as the proportion of patients that have a documented CR or PR at any time during study treatment.

Complete Response (CR) rate: Defined as the proportion of patients that have a documented CR at any time during study treatment.

Duration of Response (DOR): Defined as the time from the first achievement of PR or CR to time of PD. Patients who never achieve PR or CR are excluded. Patient who has not had disease progression/relapse at last follow-up is censored at the time of last follow-up.

Overall Survival (OS): Defined as time from initiation of study therapy to death from any cause. If a patient is alive at the last evaluation time period, survival time is censored at the time of last follow-up.

Progression-Free Survival (PFS): Defined as the time from initiation of study therapy to the first observation of disease relapse/progression or death from any cause, whichever occurs first. If the patient has not progressed relapsed or died, the patient is censored at the time of last follow-up.

Toxicity: Toxicity and adverse events will be recorded using the NCI CTCAE 5.0 scale. Observed toxicities will be summarized by type (organ affected or laboratory determination such as absolute neutrophil

count), severity (by NCI CTCAE v5.0 and nadir or maximum values for lab measures), date of onset, duration, reversibility, and attribution.

Unacceptable Toxicity: defined as one of the following AEs that is at least possibly related to study treatment:

- Any **≥ grade 3 immune-related AE (IrAE)** that does not resolve to grade ≤ 1 within 7 days with the exception of:
 - Grade 3 immune-related hepatitis if ALT or AST < 8 x ULN or total bilirubin < 5 x ULN.
 - Grade 3 asymptomatic endocrinopathy.
 - Inflammatory response attributed to local antitumor response.
 - Vitiligo or alopecia of any grade.
- Any non-hematologic **grade 4 AE** that does not resolve to grade ≤ 1 within 7 days with the exception of:
 - Grade 4 asymptomatic lipase or amylase without evidence of pancreatitis
 - Grade 4 asymptomatic laboratory abnormalities including, but not limited to, hypo- or hyperglycemia, hypo- or hypernatremia, hypo- or hyperkalemia, hypo- or hypermagnesemia, hypo- or hyperphosphatemia, or hyperuricemia that do improve within 48 hours to Grade ≤ 2 with supportive measures.
 - Inflammatory response attributed to local antitumor response.
- Any Grade 5 AE.

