12.3.3 Analysis of Anti-tumor Activity

This study will aim to obtain an estimate of the anti-tumor activity of the study combination. ORR will be calculated as the proportion of evaluable patients that have confirmed CR or PR, as defined according to the 2014 Lugano Classification, exact 95% confidence intervals will be calculated for these estimates. Response rates will also be evaluated based on number and type of prior therapy(ies). Duration of response, as well as progression-free survival and overall survival will be estimated using the product-limit method of Kaplan and Meier. As secondary endpoints, the ORR and CR rate will also be estimated according to the International Harmonization Project response criteria (Cheson 2007).⁹

Any patient treated at the RP2D, including those from the Phase 1 portion, will be included in efficacy analyses. Patients will be evaluable for efficacy assessment if they received at least one dose of pralatrexate and at least one dose of pembrolizumab and underwent at least one response assessment. As discussed in [Section 5.7](#), patients will be evaluable for efficacy if they discontinued study therapy prior to the first response assessment because of progression of disease rather than solely because of unacceptable toxicity, withdrawal of consent, or investigator's decision.

12.3.4 Safety Analysis and Stopping Rules for Excessive Toxicity or for Rapid Disease Progression

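### A response first seen on the scheduled scan after a non-progression stop is not scored for ORR but can enter DOR, and the plan conflicts on whether early toxicity stops are evaluable

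*Combined protocol and SAP*

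**What the plan says.** **Scans.** Section 11.1 schedules restaging "during cycle 4 and every 4 cycles thereafter until disease progression or off study therapy". The calendar places the Cycle 4 scan on days 15 to 21 of that cycle. Footnote r gives an end-of-treatment scan to patients who stop for progression, unless a recent scan exists. For the others: "For patients who discontinue treatment for other reasons than disease progression (e.g. for toxicity, CR): PET-CT (or CT) will not be performed at EOT". Their next scan is 12 weeks after the last. Footnote q sets the follow-up clock: "Follow-up will occur every 12 weeks (-/+ 7 days) starting from last on-treatment scan".

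**Numerator.** Section 11.2 on ORR: "Defined as the proportion of patients that have a documented CR or PR at any time during study treatment". The CR rate carries the same limit. Section 12.3.3 words it differently, with no on-treatment limit: "ORR will be calculated as the proportion of evaluable patients that have confirmed CR or PR".

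**Denominator.** Section 12.3.3 makes a patient evaluable after at least one pralatrexate dose and "at least one dose of pembrolizumab and underwent at least one response assessment". It does not say that the assessment must be on treatment. Section 12.1.2 has the same general rule. Section 5.7 replaces phase 2 patients with no tumor assessment unless progression was the cause. The next sentence of 12.3.3 then treats patients who stop before the first assessment for progression as evaluable, and contrasts them with those who stop solely for toxicity, withdrawal of consent or investigator decision.

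**DOR.** Section 11.2 runs DOR from first PR or CR to progression. Its only responder restriction is: "Patients who never achieve PR or CR are excluded". It names no on-treatment limit and no new-therapy limit.

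**The concern.** Progression is imaged at the time of stopping and response is not. For a patient who stops for toxicity before the Cycle 4 scan, the first scheduled response assessment falls off treatment. A CR on that scan fails the section 11.2 definition. The same happens to a later stopper whose response develops after the last on-treatment scan.

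The protocol gives reasons to expect some such responses. Appendix C says that responses to immunotherapy can come later than those to cytotoxic drugs, and section 8.1.4 gives pembrolizumab a half-life of 22 days.

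Three things are at stake: a primary ORR that can be lowered by toxicity stops rather than by lack of activity; a stage 1 count in which one unscored responder can decide a 0-of-7 stop; and a DOR estimated in a different set of responders from ORR.

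**Working it through.** **1. The plan's own figures (section 12.1.2).**
- Chance of at least one response in 7 at ORR 35%: 1 − 0.65^7 = 0.951. The plan states at least 95%.
- Standard error at n = 24, √(p(1−p)/24): 9.35% at p = 0.30 or 0.70, and 10.21% at p = 0.50. The plan states 9.4% to 10.2%.
- Widest exact 95% interval, at 12/24: 29.1% to 70.9%, width 41.8%. The plan states 42%.

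All three reproduce.

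**2. Timing.** Three 21-day cycles take 63 days, so without delay the Cycle 4 scan falls on study days 63 + 15 = 78 to 63 + 21 = 84. Restaging every 4 cycles is 84 days, or 12 weeks. For a patient with no on-treatment scan, the last scan is the baseline one, between day −28 and day 1. Twelve weeks later is about day −28 + 84 = 56 to day 1 + 84 = 85. The post-treatment scan therefore comes at about the same calendar time as the Cycle 4 scan, or earlier.

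**3. How each type of patient is scored.**

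| Patient | Numerator under 11.2 | Denominator |
|---|---|---|
| Stops after an on-treatment CR or PR | counts | in |
| Stops after Cycle 4 scan, first response on the post-treatment scan | does not count | in |
| Stops for toxicity before Cycle 4 scan, response on the post-treatment scan | does not count | in by the general rule; out if the next sentence of 12.3.3 governs |

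The second and third patients both meet the DOR definition as written.

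**4. Size if the affected patients stay in the denominator.** Let d be the share of the denominator that stops with no response yet imaged on treatment and is scored as non-responder. Assume that these patients would have responded at the same rate p as the rest, with the response first seen on the post-treatment scan. Expected scored ORR is p(1−d), and the stage 1 pass probability is 1 − (1 − p(1−d))^7. The documents give no value for d; the range below is an assumption.

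| d | Scored ORR, p = 35% | Stage 1 pass, p = 35% | Scored ORR, p = 50% |
|---|---|---|---|
| 0% | 35.0% | 95.1% | 50.0% |
| 5% | 33.3% | 94.1% | 47.5% |
| 10% | 31.5% | 92.9% | 45.0% |
| 15% | 29.8% | 91.6% | 42.5% |
| 20% | 28.0% | 90.0% | 40.0% |

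Per patient among 24, the loss is p/24: 0.35/24 = 1.5 points, or 0.50/24 = 2.1 points. Three such patients give 0.35 × 21/24 = 30.6%, or 0.50 × 21/24 = 43.8%.

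**5. Size if early toxicity stops are non-evaluable and replaced.** The expected ORR stays at p and the pass probability at 95.1%, but only if stopping early for toxicity is unrelated to response. Otherwise the estimate describes only patients who tolerated treatment long enough to be scanned. The documents do not allow this to be sized.

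**The case against.** The strongest reply is that this is a wording gap of unknown effect, and that several stronger conclusions do not follow. Much of that stands.

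- A reader might infer that anyone who stops for toxicity cannot be a responder. That is wrong. A CR or PR on any on-treatment scan counts, the calendar allows extra procedures when clinically indicated, and section 5.10 lets a patient continue on one agent while the other is delayed for toxicity.
- A reader might infer that early toxicity stops are certainly in the denominator. The contrast in 12.3.3 implies that they are not evaluable. Against that, the sentence concerns stops before a first assessment and refers to 5.7, which turns on having no assessment at all; a patient with a footnote r scan has one. Neither reading is secure, and each has a cost: a forced non-response, or selective removal.
- A reader might take the 21% rate of grade 3 or 4 mucositis (section 2.3) or the 33% toxicity limit (section 12.3.4) as the rate of stopping before imaging. Neither is one. The first is an adverse-event rate, and Table 6.4.1 provides for dose omission and reduction at grade 3, and for possible resumption of pembrolizumab after grade 4. The second is an accrual-halt threshold for events at any time during treatment.
- A reader might infer that the plan's 95% figure is wrong. It is correct for ORR as section 11.2 literally defines it. The shortfall appears only against a true rate that includes responses first imaged after treatment.
- A reader might infer that the plan deliberately counts responses to a later drug in DOR. The text is silent: footnote q follows patients until progression or off study, and 5.11 sets no rule for new therapy. DOR merely fails to exclude such responses.

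The reply does not remove the mismatch between footnote r and section 11.2, the conflict over evaluability, or the difference between the ORR and DOR responder sets.

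**Conclusion.** The point holds as a mismatch that should be corrected. A CR or PR first seen on the scheduled post-treatment scan is lost to ORR and CR rate under 11.2, while DOR can include it. For stops before Cycle 4, the plan supports both a forced non-response and an exclusion, and 12.3.3 does not repeat the on-treatment limit of 11.2.

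The effect is probably below one standard error (about 10 points): about 1.5 points of expected ORR per affected patient among 24 at a true 35%, and a stage 1 pass probability of 94.1%, 92.9% or 90.0% at an assumed 5%, 10% or 20%. It runs in one direction, and a larger sample would not remove it. These figures rest on the assumed shares, on affected patients responding like the others, and on their staying in the denominator.

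**What to change.** 1. In 11.2, count for ORR and CR rate a CR or PR documented from first dose through the first scheduled scan after the last dose (the footnote r scan), before Lugano progression and before any new anticancer therapy. Use the same definition in 12.3.3.
2. In 5.7, 12.1.2 and 12.3.3, state that this scan makes a patient evaluable whatever the reason for stopping, and reword the sentence in 12.3.3 that contrasts progression with toxicity stops.
3. Apply the same rule to the stage 1 count of 7.
4. Restrict DOR to patients counted as ORR responders.
5. In footnote q, name the baseline scan as the anchor for patients with no on-treatment scan.

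The cost is wording only. The scan is already scheduled, and the calendar already records post-study anticancer therapy. The downside is that a response imaged up to about 12 weeks after the last dose is credited to the regimen.
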